8.3 Serious Adverse Events

8.3.1 Serious Adverse Event Definition

An event is defined a serious adverse event if it:	Guidance
results in death	Any event resulting in a fatal outcome must be fully documented and reported, including deaths occurring within 4 weeks after the treatment ends and irrespective of the causal relationship to the IMP. The death of a subject enrolled in a trial is per se not an event, but an outcome.
is life-threatening	The term life-threatening refers to an AE in which the subject was at immediate risk of death at the time of the event. It does not refer to an event that may have caused death if it were more severe.
requires inpatient hospitalization or prolongation of existing hospitalization	The term hospitalization means that the subject was admitted to hospital or that existing hospitalization was extended as a result of an event. Hospitalization describes a period of at least 24 hours. Overnight stay for observation, stay at emergency room or treatment on an outpatient basis do not constitute a hospitalization. However, medical judgment must always be exercised and, when in doubt, the case should be considered serious (i.e., if case fulfills the criterion for a medically important event). Hospitalizations for administrative or social purposes do not constitute an SAE. Hospital admissions and/or surgical operations planned before trial inclusion are not considered adverse events, if the illness or disease existed before the subject was enrolled in the trial, provided that the condition did not deteriorate during the trial.
results in persistent or significant disability/incapacity	Disability/incapacity means a substantial disruption of a person's ability to conduct normal life functions. In doubt, the decision should be left to medical judgement by the investigator.
is a congenital anomaly/birth defect	Congenital anomaly/birth defect observed in any offspring of the subject conceived during treatment with the IMP.

An event is defined a serious adverse event if it:	Guidance
is an important medical event	
Important medical events are events that may not be immediately life-threatening or result in death or hospitalization but may jeopardize the subject or may require intervention to prevent one of the other outcomes listed in the definition above. Examples of important medical events include AEs that suggest a significant hazard, contraindication or precaution, occurrence of malignancy or development of drug dependency or drug abuse. Medical and scientific judgement should be exercised in deciding whether events qualify as medically important.
 
Important medical events include any suspected transmission of an infectious agent via a medicinal product. Any organism virus or infectious particle (e.g., prion protein transmitting Transmissible Spongiform Encephalopathy), pathogenic or non-pathogenic, is considered an infectious agent. A transmission of an infectious agent may be suspected from clinical symptoms or laboratory findings indicating an infection in a subject exposed to a medicinal product.

8.3.2 Collection, Recording and Reporting of Serious Adverse Events

SAE Reporting by the Investigator

An SAE must be reported **immediately** to Ferring Pharmaceuticals as soon as it becomes known to the investigator and not later than within 24 hours of the investigator's knowledge of the occurrence of an SAE.

The investigator is responsible for submitting the completed SAE Report Form with the fullest possible details to the local safety officer at Ferring Pharmaceuticals, Inc. by fax **within 24 hours** of his/her knowledge of the SAE **and submit all related follow-up information no later than 3 calendar days** using the contact details below:

Safety Fax: [REDACTED]

Safety E-mail: [REDACTED]

For questions contact: Medical Monitor, [REDACTED]

E-mail: [REDACTED]

Contact Number: [REDACTED]

Completion of the Demographics, Adverse Events Log, Medical History Log and Concomitant Medication Log is **mandatory** for initial reports and for follow-up reports if any changes have been made since the initial report.

Additional information relevant to the SAE such as hospital records, results from investigations, e.g., laboratory parameters (that are not already uploaded in the eCRF), invasive procedures, scans and x-rays, and autopsy results can be faxed or scanned and e-mailed to Ferring Pharmacovigilance using the contact details in the section above. In any case, this information must be supplied by the investigator upon request from Ferring. On any copies provided, such details such as subject's name, address, and hospital identification number should be concealed and instead subject number should be provided.

The investigator will supply Ferring and the IEC/IRB with any additional requested information such as results of post-mortem examinations and hospital records.

Expedited Reporting by Ferring

Ferring will report all adverse events that are **serious, unexpected and with a reasonable possible causality to the IMP** as judged by either the investigator or Ferring to the relevant parties within the stipulated timelines.

The expectedness is assessed by Ferring according to the Investigator's Brochure.¹⁴

SAEs will be considered reportable regardless of whether or not the IMP was used in accordance with the provisions in the protocol, Investigator's Brochure and labelling.

8.4 Follow-up of Adverse Events and Serious Adverse Events

8.4.1 Follow-up of Adverse Events with Onset during the Trial

During the trial, the investigator must follow-up on each adverse event until it is resolved or until the medical condition of the subject is stable.

After the subject's last visit, the investigator must follow-up on any adverse event classified as serious or considered to have a reasonable possible causality to the IMP until it is resolved or until the medical condition of the subject is stable. All such relevant follow-up information must be reported to Ferring. If the event is a chronic condition, the investigator and Ferring may agree that further follow-up is not required.

8.4.2 Collection of Serious Adverse Events with Onset after Last Visit

If an investigator becomes aware of an SAE after the subject's last visit, and he/she assesses the SAE to have a reasonable possible causality to the IMP, the case will have to be reported to Ferring, regardless of how long after the end of the trial this takes place.

8.5 Unanticipated Adverse Device Effects

The definition of an Unanticipated Adverse Device Effect per FDA regulations is as follows:

Unanticipated adverse device effect is any serious adverse effect on health or safety, any life-threatening problem or death caused by or associated with a device, if that effect, problem, or death was not previously identified in nature, severity, or degree of incidence in the application; or any other unanticipated serious problem associated with a device that relates to the rights, safety, or welfare of subjects. Adverse device effects should be collected and assessed as for adverse events above.

The investigator should collect, record, and assess any UADE similar to the directions for adverse events above. The investigator must report the adverse device effect to Ferring as described in Section 8.3.2 above on the device report form. In the circumstance that a serious adverse event and an UADE occur together, the SAE form should be completed and the device information also included.

9 STATISTICAL METHODS

Details of the statistical methodology will be provided in a separate Statistical Analysis Plan.

9.1 Determination of Sample Size

The sample size was determined based on the original fixed parallel group study design. The true ovulation rate for LutrePulse OmniPod SC 20 µg, 15 µg, 10 µg, and placebo was assumed to be 70%, 65%, 60%, and 1%, respectively. Under these assumptions, a sample size of 14 subjects per group (total 56 subjects) will provide at least 80% power to detect differences between LutrePulse OmniPod SC 20 µg and placebo, 15 µg and placebo, and 10 µg and placebo in ovulation rate separately using the stratified one-sided Fisher's exact tests¹⁹ at an overall one-sided significance level of 0.025 with the closed testing procedure (Kong et al., 2005)¹⁸ to be used for the primary efficacy analysis.

Approximately 60 subjects will be randomized, assuming up to 4 subjects may be ineligible for the full analysis set (FAS).

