5.4 Blinding / Unblinding

5.4.1 Blinding

To ensure blinding, subjects assigned to placebo will be randomized to 1 of 3 placebo "dose" groups – 10 µg, 15 µg, or 20 µg according to a computer-generated randomization list prepared for all trial sites. Study personnel involved in the conduct of the study will be blinded to the assigned drug product (active or placebo) regardless of dose. The OmniPod Manager will display the dose once it has been programmed for a subject, regardless of active or placebo assignment.

All eligible subjects will be randomly assigned at least 5 days before Treatment Day 1 (7 days for sites in Canada), based on the computer-generated randomization list. The first 15 eligible subjects will be randomly assigned to 1 of 3 treatment arms: LutrePulse OmniPod SC 10 µg, LutrePulse OmniPod SC 20 µg, or OmniPod SC placebo in a 1:1:1 ratio. The subsequent 25 eligible subjects will be randomly assigned to LutrePulse OmniPod SC 10 µg, LutrePulse OmniPod SC 15 µg, LutrePulse OmniPod SC 20 µg, or OmniPod SC placebo in a 1:2:1:1 ratio. The rest of the eligible subjects will be randomly assigned to LutrePulse OmniPod SC 10 µg, LutrePulse OmniPod SC 15 µg, LutrePulse OmniPod SC 20 µg, or OmniPod SC placebo in a 1:1:1:1 ratio. To maintain blinding for subjects and the unblinded coordinator to the assigned drug product, the placebo subjects will be randomly assigned to the equivalent dosing setting in the Manager for 10 µg /pulse or 20 µg /pulse for the first 15 eligible subjects and 10 µg /pulse, 15 µg /pulse, or 20 µg /pulse for

the other randomization schemes. The randomization dose assignment (dose only) will be available to the OmniPod Manager programmer (unblinded coordinator), but not to any other site personnel involved in the conduct and evaluation of the study until the study database is declared clean and is released to the statistician.

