Conversely, when success on the primary efficacy analysis is declared at an interim analysis, if the response rate in the low-dose arm meets the condition in inequality (1), then the trial is completed at this point (outcome #4) with dose selection performed using the ED80 rule (see below).

In the case the primary efficacy analysis is successful, but the response rate in the low-dose arm is within 20% from the combined low- and high-dose success rate, the trial is not stopped immediately. Rather, the trial will continue to enroll additional patients into the low-, middle- and high-dose arms to further assess dose responses (outcome #3).

Finally, the trial may terminate (outcome #5) as a result of a low predictive probability of success (<0.05) given the data collected at the interim analysis.

At the end of the study, for a trial that achieves efficacy success, the dose to be selected is the ED80 dose, defined as the lowest dose that retains at least 80% of the largest treatment effect, i.e.

$$(R_{ED80} - R_{placebo}) \ge (R_{maximum} - R_{placebo}) \times 0.8, \tag{2}$$

where $R_{maximum}$ is the observed ovulation rate in the most effective dose arm, $R_{placebo}$ is the observed ovulation rate in the placebo arm, and R_{ED80} is the observed ovulation rate in the selected dose arm.

A flow diagram is presented in Figure 1 of Section 15.2.1 to illustrate the decision tree for the two-interim adaptive design. Further details, such as the criteria for efficacy success using the group sequential method, the Bayesian predictive probability of future success to determine futility, the

rationales behind the 20% threshold to drop low dose, the ED80 dose-selection rule and dose-response evaluations are described in Section 9.2.1.1. Simulation results to assess operating characteristics of the design are given in Section 15.2.

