In this scenario, all doses are highly effective. The power of the trial exceeds 99%, with most trials declaring early success at an interim. Of the 10000 simulated trials, 9332 trials (93.3%) declared early success at the first interim. Of those, 2782 trials also dropped the low dose at the same time (ending the trial), and 6550 dropped the placebo and continued with only the investigational arms. Of those trials, 570 trials dropped the low dose at the second interim, while the remaining 5980 trials continued to the final analysis with all investigational arms. The average sample size reflects the tendency of trials to declare early success, with the placebo arm having, on average, 9.2 subjects (smaller than the investigational arms). In truth, the low dose is quite effective, so it is rarely dropped, and it is selected as the ED80 in 45.6% of trials.

Statistical Analysis Plan

Trial Outcomes

Pr(Success)	Pr(Early Win)	Pr(Early Futility)
0.999	0.990	0.000

Mean Sample Size

Placebo	Low	Mid	High	Total
9.2	13.1	13.1	13.1	48.6

None	Low	Mid	High
0.001	0.456	0.356	0.188

[figure not shown]
Figure 7 Operating Characteristics for Scenario 1: 0.01, 0.60, 0.65, 0.70

Date: 07 Dec 2017 E-Statistical Analysis Plan-21977; Ver. 1.0 Supersedes: None Page 43 of 59

Scenario 2: 0.01, 0.50, 0.65, 0.75

In this scenario, there is a larger range between the low dose and high dose response rates. The low dose response rate is exactly 20% lower than the combined middle and high doses.

This scenario also has quite high power, and is more likely to stop the trial early due to declaring early success and dropping the low dose. Roughly half of the trials (50.5%) ended at the first interim, with an additional 45% declaring early success at the first interim, but continuing the trial (without the placebo arm). The average sample size tends to be smaller in this scenario, since more trials end early. The middle dose is most likely to be selected as the ED80.

Pr(Success)	Pr(Early Win)	Pr(Early Futility)
1.000	0.994	0.000

Mean Sample Size

Placebo	Low	Mid	High	Total
9.2	11.7	11.7	11.7	44.2

None	Low	Mid	High
0.000	0.182	0.482	0.335

[figure not shown]
Figure 8 Operating Characteristics for Scenario 2: 0.01, 0.50, 0.65, 0.75

Date: 07 Dec 2017 E-Statistical Analysis Plan-21977; Ver.1.0 Supersedes: None Page 45 of 59

Scenario 3: 0.01, 0.20, 0.60, 0.60

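### The stated 80% power for each dose versus placebo belongs to the superseded fixed design; the adaptive rules do not deliver it, least of all for a stratified 15 µg comparison

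*Protocol*

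**What the plan says.** Protocol 9.1 opens with the statement that "The sample size was determined based on the original fixed parallel group study design". The ovulation rate for 20, 15 and 10 µg and placebo "was assumed to be 70%, 65%, 60%, and 1%, respectively". On that basis "a sample size of 14 subjects per group (total 56 subjects) will provide at least 80% power to detect differences" for each dose separately, with one-sided Fisher tests stratified by randomization scheme, an overall one-sided level of 0.025 and a closed testing procedure. The protocol adds that this procedure is meant for the primary efficacy analysis. The synopsis repeats the text, and SAP 3.2 repeats it without that last clause.

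The primary objective (Protocol Section 2, SAP 2.1) is still each dose against placebo, and SAP 3.3 names the three single-dose comparisons with pooled placebo. The primary test in Protocol 9.6.2 and SAP 9.2.1 is different: pooled 15 and 20 µg against placebo at p < 0.0131 per look.

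If the pooled test succeeds at an interim look and the low dose is not clearly worse, SAP Section 9 says "the trial will continue to enroll additional patients into the low-, middle- and high-dose arms to further assess dose responses (outcome #3"; placebo receives nobody further. If the low dose is clearly worse, the trial stops. SAP 15.2.3, Scenario 1, uses the planning rates and reports first-look success in 9332 of 10000 trials, "with the placebo arm having, on average, 9.2 subjects (smaller than the investigational arms").

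On allocation, Protocol 5.4.1 says "The first 15 eligible subjects will be randomly assigned to 1 of 3 treatment arms" (10 µg, 20 µg, placebo). The next 25 are allocated 1:2:1:1 to 10, 15, 20 µg and placebo, and the rest equally.

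**The concern.** The sample-size sections give one power figure, per dose, for "a sample size of 14 subjects per group (total 56 subjects"). The adaptive rules usually do not produce that sample size: at the planning rates placebo ends at 9 in most trials. The 15 µg arm is hit hardest. It was not randomized in scheme 1, so that scheme's placebo subjects cannot enter a comparison stratified by scheme. Subjects on 15 µg randomized in scheme 3 after placebo closes have no placebo subject in their stratum either.

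What is at stake is interpretation. A reader who trusts the section would take a non-significant single-dose result as a failed comparison with adequate power. Under the current rules it may only reflect how few placebo subjects were available.

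**Working it through.** **Inputs.** Rates 0.01, 0.60, 0.65, 0.70 (Protocol 9.1). Exact test stratified by scheme (Protocol 9.6.2). Looks at about 9 and 12 per arm, pooled threshold 0.0131 (Protocol 9.6.1 and 9.6.2). Allocation from Protocol 5.4.1: scheme 1 gives 5 each on 10 µg, 20 µg and placebo; scheme 2 gives 5, 10, 5, 5 on 10, 15, 20 µg and placebo; scheme 3 is equal. Assumed here: one-sided 0.025 per pair (an upper bound for any closed test), no loss from the full analysis set, and, until step 6, nobody randomized while interim data mature.

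**1. The plan's own figure.** Fixed 14 v 14, exact enumeration:
- Unstratified: 96.4%, 98.4%, 99.4% for 10, 15, 20 µg.
- Stratified: 96.3%, 90.3%, 99.3%. For 15 µg the informative strata are 10 v 5 and 4 v 4.

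The statement of at least 80% is reproduced for the fixed design.

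**2. The first look.** Pooled 18 v 9 at p < 0.0131, enumerated exactly, succeeds with probability 93.4%; the SAP prints 93.3%.

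**3. Who counts in a stratified 15 µg test.** A stratum with only one of the two arms contributes nothing. With placebo closed at 9, five placebo subjects sit in scheme 1 and four in scheme 2. Only those four count, against the 15 µg subjects of scheme 2. With a first look at 10 per arm the split is 10 v 5.

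**4. Hand check.**
- 9 v 4, no placebo responders: 7 of 9 gives p = C(9,7)/C(13,7) = 36/1716 = 0.021; 6 of 9 gives 84/1716 = 0.049. Power = P(Bin(9, 0.65) ≥ 7) × 0.99^4 = 0.337 × 0.961 = 0.32.
- 10 v 5: 7 of 10 gives p = 120/6435 = 0.0187. Power = 0.514 × 0.951 = 0.49.
- 8 v 4, by the same enumeration: 16%.

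**5. Whole adaptive trial, stratified test at 0.025** (20,000 simulated trials per setting; ranges cover an unstratified or stratified pooled test at the looks):

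| Scheme-2 split at first look, 15 µg v placebo | 10 µg | 15 µg | 20 µg |
|---|---|---|---|
| 8 v 4 (list allocation at subject 35) | 72-73% | 27-29% | 92-95% |
| 9 v 4 (exactly 9 per arm) | 72-73% | 31-33% | 92-94% |
| 10 v 5 (list allocation at subject 40) | 81% | 51-52% | 94-95% |

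Futility stopping was left out because Scenario 1 reports it as 0.000. Success on the pooled test is 0.999 or higher in every setting.

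**6. Sensitivity.**
- *Overrun.* Let 1, 2 or 3 scheme-3 subjects per arm, placebo included, be randomized before placebo closes. Stratified 15 µg power at 10 v 5 plus these pairs rises from 49% to 64%, 76% and 85%.
- *Unstratified test.* 14 v 9 gives 82%, 90%, 95% for 10, 15, 20 µg; 15 v 9 gives 88%, 94%, 97%. Over the whole adaptive trial the values are 75-81%, 91-94% and 98%.
- *Stricter level.* At 0.0131, stratified 15 µg power over the adaptive trial is 12-26%.

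**The case against.** The case on the other side is substantial. The text says where the sample size came from, and for that design the figure is right. The current primary analysis tests only the pooled doses; SAP 9.2 gives no single-dose ovulation test and no alpha for one, and dose selection uses observed rates through the ED80 rule. The pooled-test power at the planning rates is already in SAP 15.2.3. Overrun is also plausible: Protocol 9.6.1 times the looks by enrolment, 9.9 by completion, treatment can last about seven weeks, and no enrolment pause is stated.

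All of this stands, and it rules out several stronger readings that a reader might infer:
- *The 80% is an arithmetic error.* It is not (step 1).
- *Eighty percent power needs 14 placebo subjects.* It does not: 9 placebo with 14-15 active give 82-97% unstratified. The large 15 µg loss comes from early placebo closure combined with stratification.
- *Every dose falls short.* 20 µg stays above 90% at 0.025, and 10 µg reaches about 81% with a first look at 10 per arm.
- *The primary test is underpowered.* The pooled test has 0.999.
- *15 µg power is 31%.* That single value rests on one stratum split, no overrun and a stratified test.

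None of this makes the retained per-dose figure true of the current design. The documents nowhere say that it has lapsed, and the protocol still ties the closed procedure to the primary analysis while the objective remains per dose.

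**Conclusion.** The concern holds as a labelling and reporting fault. The per-dose statement of at least 80% describes the fixed design and has not been shown for the adaptive one. Without overrun, and with a stratified test at one-sided 0.025, 15 µg falls short of 80% by about 47-53 points with a first look at 9 per arm (80 minus 27-33) and by about 28-29 points at 10 per arm. For 10 µg the result runs from about 8 points short to just above 80%. Part of that loss arises without stratification, since 2782 of the 10000 Scenario 1 trials stop with every arm at 9.

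The 15 µg figure rests on the interim stratum split (block size is not given), the absence of overrun and the choice of test. Relaxing the second or third can restore 80% or more. The evidence supports a range, not a replacement point value. The conclusion on the pooled primary test does not change.

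**What to change.** In Protocol 9.1, the synopsis and SAP 3.2:

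1. State that the per-dose 80% figure and the closed testing procedure applied only to the superseded fixed design.
2. Give the power of the current pooled 15 and 20 µg test under the adaptive rules as the design's power (0.999 in SAP Scenario 1).
3. Report per-dose power from the existing simulation as a range over the interim stratum split, enrolment overrun and the test used.
4. Add that a non-significant single-dose comparison after early placebo closure is not evidence of no effect.

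The cost is wording in three places and one further simulation output, with no extra patients. The downside is a less favourable stated figure.

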9.2 Subject Disposition

The number and percentage of randomized subjects treated with IMP, prematurely discontinued, and completing the study will be summarized. All post-baseline discontinuations will be summarized by reason for discontinuation. The number of subjects screened and not randomized will be presented.

9.3 Protocol Deviations

The criteria for protocol deviations considered major with the implication of data exclusions from the per-protocol analysis set will be determined before database lock.

9.4 Analysis Sets

9.4.1 Intent-to-Treat (ITT) Analysis Set

All randomized subjects will be included in the ITT analysis set.

9.4.2 Full Analysis Set (FAS)

All randomized subjects who are included in the ITT analysis set and received at least 14 days of study drug for pituitary priming will be included in the FAS.

9.4.3 Modified Intent-to-Treat (mITT) Analysis Set

All randomized subjects who received at least one (1) pulsatile injection delivery of study drug will be included in the mITT Population.

